6.2 Serious Adverse Events (SAEs) and Serious Adverse Drug Reactions (SADRs)

A Serious Adverse Event is defined as any untoward medical occurrence that at any dose results in:

- 1) Death
- 2) A life-threatening situation (subject was at risk of death at the time of the event. This does not refer to an event that might have caused death if it was of greater intensity.)
- 3) New in-patient hospitalization or prolongation of an existing hospitalization
- 4) Persistent or significant disability or incapacity
- 5) Congenital anomaly or birth defect
- 6) Important medical events that may not result in death, be life-threatening, or require hospitalization but may jeopardize the subject and may require medical or surgical intervention to prevent one of the above outcomes (based upon appropriate medical judgment), e.g., allergic bronchospasm requiring intensive treatment in an emergency room or at home, blood dyscrasias or convulsions that do not result in inpatient hospitalization, or the development of drug dependency or drug abuse.

Medical and scientific judgment should be exercised in deciding whether other conditions should also be considered serious, such as important medical events that may not be immediately life-threatening or result in death or hospitalization but may jeopardize the subject or may require intervention to prevent one of the other outcomes listed above. These should also be considered serious. Follow up information regarding SAEs will be pursued until the event has resolved (with or without sequelae), until death, or until 30 days after the final study visit (whichever comes first.). For any deaths where there is uncertainty about the cause of death, site investigators may request an autopsy if appropriate.

6.3 Reporting Serious Adverse Events (SAE)

Any SAE, including death due to any cause, which occurs between enrolment and the final follow up visit whether or not related to the study drug, must be reported immediately (within 1 business day of the study site's knowledge of the event). The report will contain as much available information concerning the SAE to enable a report to be produced that satisfies regulatory reporting requirements.

The term "severe" is often used to describe the intensity (severity) of a specific event (as in mild, moderate, or severe pain); the event itself, however, may be of relatively minor medical significance (such as severe headache). By contrast, the term "serious" is used to describe an event based on an event outcome or

actions usually associated with events that pose a threat to a subject's life or functioning. Seriousness (not severity) serves as a guide for defining regulatory reporting obligations.

For all collected SAE's, the clinician who examines and evaluates the subject will determine the event's causality based on temporal relationship and his/her clinical judgment. The degree of certainty about causality will be graded using the categories below:

Definitely Related: There is clear evidence to suggest a causal relationship, and other possible contributing factors can be ruled out.

Probably Related: There is evidence to suggest a causal relationship, and the influence of other factors is unlikely.

Possibly Related: There is some evidence to suggest a causal relationship. However, the influence of other factors may have contributed to the event.

Unlikely: A clinical event, including an abnormal laboratory test result, whose temporal relationship to drug administration makes a causal relationship improbable and in which other drugs or chemicals or underlying disease provides plausible explanations

Not Related: The SAE is *completely independent of study drug administration, and/or evidence exists that the event is definitely related to another etiology.*

Pre-existing conditions should be recorded upon patient enrolment (including start date of the condition, and severity - mild, moderate, severe). After the patient signs the informed consent form, any worsening of these conditions would be recorded.

Any new conditions would be recorded including date of onset, date of resolution, severity (mild, moderate, severe, or serious as defined above) and possible relationship to study drug or procedure. As part of the source notes, follow up clinical assessments, laboratory tests, ECGs and diagnostic imaging related to adverse event should be documented.

6.4 Reporting of Serious Unexpected Adverse Drug Reactions (SUADRs)

The PI (or an authorized representative) is responsible for submitting reports of SUADRs to the appropriate regulatory body within the required reporting period. All investigators participating in ongoing clinical studies with the study drug will be notified by the Coordinating Center (or an authorized representative) of all SUADRs that require prompt submission to the REB/IRB. Investigators are responsible for notifying the REB/IRBs in writing of the SUADRs within the required reporting timelines. Copies of the notification will be maintained by the investigator in the study documentation files. Sites will receive detailed reporting guidelines for the SAE reporting process.

7 STATISTICAL ANALYSIS AND SAMPLE SIZE CALCULATION:

7.1 Sample Size Estimation

The goal of this study is to estimate biologically plausible effects as a result of PCSK9 inhibition in a population of patients with type 2 diabetes and microvascular dysfunction. As a result, this will be treated as a “signal” finding trial – and used as preliminary data to support a formal sample size estimation for a larger clinical trial. We anticipate that 40 subjects will be required to provide sufficient data to adequately identify robust changes in the large range of biocellular markers being assessed.

7.2 Statistical Analysis

As we seek to address both early and late changes in biocellular responses as a result of PCSK9i, we will compare changes between week 2 and week 12 with baseline. We will also compare week 2 with week 12 to identify how the expected rheological changes may impact biocellular responses.

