Furthermore, oscillatory shear stress increases the activation of pro-inflammatory signaling pathways and reduces activation of anti-inflammatory pathways. As an exploratory aim, we will measure low shear blood viscosity to examine the associations between baseline and on-trial change in low shear blood viscosity with inflammatory mediators. The data on blood viscosity will also be used to support our larger aim concerning the putative role of PCSK9 inhibition on cardiac microvascular dysfunction, as blood flow in the microcirculation is highly dependent on changes in blood viscosity.

Our aim is to define how PCSK9 inhibition alters the circulating monocyte populations and to systematically profile the transcriptional and proteomic responses to TLRs and how these responses are modulated by PCSK9 inhibition in the peripheral blood mononuclear cells (PBMC) clinical samples and relate these molecular signatures to clinical and imaging variables. The overall rationale for the work proposed is to understand the molecular mechanisms through which PCSK9 and circulating lipoproteins orchestrate TLR response in circulating monocytes. The outcome measures for this aim include PBMC subset analysis and transcriptional and proteomic analysis of inflammatory signaling pathways in

response to TLR stimulation. After the proposed studies for this aim have been completed, *it is our expectation that we will have defined the molecular pathways through which PCSK9 modulates inflammatory responses in circulating monocytes and how these molecular signatures relate to clinical variables known to be important in CVD risk stratification.*

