1.1.1. Primary Objective

Determine the ACUTE and SHORT-TERM effects of PCSK9 inhibition with evolocumab on biocellular markers of inflammation, immune mediated thrombosis and rheology. The data from this trial will be used to support a clinical trial to assess the role of PCSK9 inhibition in type 2 diabetes patients with microvascular dysfunction.

1.1.2. Secondary Objective:

- a) To define the association between PCSK 9 concentrations and immune-related phenotype.
- b) To define the association between Lp(a) concentrations, oxidized phospholipids (OxPL), ApoB, biocellular markers of inflammation, tissue factor and immunothrombosis.

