3. STUDY DESIGN

3.1. Study Overview

This is a double-blind, randomized, placebo-controlled, parallel group Phase IV study with two treatment arms: evolocumab SC 420 mg/dL QM or matching placebo. The population will include men and women of non-child-bearing potential with documented CAD and type 2 diabetes.

Approximately 100 subjects will be screened in order to keep 40 subjects to complete the study. Subjects will be followed for 12 weeks during the treatment phase, maintaining the double-blind throughout. Assessments of ACUTE and SHORT-TERM effects of PCSK9 inhibition with evolocumab on biocellular markers of endothelial function will be measured at baseline, Week 2, and Week 12. Safety assessments will be undertaken at each study visit. Subjects whose maximally tolerated dose of statin is no type or dose (i.e. determined to be statin intolerant by primary investigator) must be randomized fairly between 2 treatment arms to prevent selection bias.

Subjects should continue on their stable dose of anti-hyperglycaemic therapies during the course of the study. However, it is important that the haemoglobin A1c (HbA1c) does not rise above 10% and that the patient does not develop severe hypoglycaemia or frequent episodes of mild-moderate hypoglycaemia, as defined by the Canadian Diabetes Association 2008 Clinical Practice Guidelines for the Prevention and Management of Diabetes.¹³

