4 SCHEDULE OF STUDY PROCEDURES

Screening assessments and study procedures outlined in this section and in Table 1 can only be performed after obtaining written informed consent.

All on-study visits and dosing should be scheduled from Day 1 (first IP administration). For example, the Week 2 visit is 2 calendar weeks after the study Day 1 visit, which corresponds to study Week 2. When it is not possible to perform the study visit at the specified time point, the visit should be performed within the visit window specified in Table 1. If a study visit is missed or late, including visits outside the visit window, subsequent visits should resume on the original visit schedule. Missed assessments at prior visits should not be duplicated at subsequent visits. With the exception of screening, all study procedures for a visit should be completed on the same day if possible.

Visit 1: Screening

- Written informed consent
- Demographics
- Medical history
- Vital signs
- 12 lead ECG measurement
- Concomitant therapy
- Dietary instruction; medication compliance reminder
- Physical examination
- Body height, waist circumference
- Body weight
- Seattle Angina Questionnaire 7 (SAQ7)
- Laboratory assessments: TSH, hematology (CBC), blood chemistry (creatinine/eGFR and electrolytes), Liver Function Tests (ALT, AST), creatinine/eGFR, HbA_{1c}, local lipid panel, urine albumin to creatinine ratio (ACR), urine pregnancy test (if female of child bearing potential)

Visit 2 (Randomization) 7-28 days after Screening

- Review for AEs/SAEs/CV events
- Concomitant therapy
- Vital signs
- Dietary instruction; medication compliance reminder
- Randomization
- Seattle Angina Questionnaire 7 (SAQ7)
- Laboratory assessments: fibrinogen, whole blood viscosity analysis, NMR lipoprotein subclass analysis, Apo B, lipoprotein (a), biocellular marker analysis, Oxidized lipid Analysis
- DNA/mRAN test for lipoprotein and inflammatory polymorphisms that may influence the response to therapy (the specimens will be stocked at site and the tests will be performed later).
- SC IP administration, QM (in-clinic) and 30 minute post-injections observation

Visit 3 (Week 2) ±4 days

- Review for AEs/SAEs/CV events
- Concomitant therapy
- Vital signs

- Dietary instruction; medication compliance reminder
- Seattle Angina Questionnaire 7 (SAQ7)

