- Laboratory assessments: hematology (CBC), blood chemistry (creatinine/eGFR, electrolytes), Liver Function Tests (ALT/AST), fibrinogen, whole blood viscosity analysis, NMR lipoprotein subclass analysis, Apo B, lipoprotein (a), biocellular marker analysis, Oxidized lipid Analysis

Visit 4 (Week 4) ±7 days

- Review for AEs/SAEs/CV events
- Concomitant therapy
- Vital signs
- Dietary instruction; medication compliance reminder
- Seattle Angina Questionnaire 7 (SAQ7)
- SC IP administration, QM (in-clinic) and 30 minute post-injections observation

Visit 5 (Week 8) ±7 days

- Review for AEs/SAEs/CV events
- Concomitant therapy
- Vital signs
- Dietary instruction; medication compliance reminder
- Seattle Angina Questionnaire 7 (SAQ7)
- SC IP administration, QM (in-clinic) and 30 minute post-injections observation

Visit 6 (Week 12) ±7 days

- Body height, waist circumference
- Body weight
- Review for AEs/SAEs/CV events
- Concomitant therapy
- Dietary instruction; medication compliance reminder
- Seattle Angina Questionnaire 7 (SAQ7)
- Laboratory assessments: hematology (CBC), blood chemistry (creatinine/eGFR, electrolytes), Liver Function Tests (ALT/AST), fibrinogen, whole blood viscosity analysis, NMR lipoprotein subclass analysis, Apo B, lipoprotein (a), biocellular marker analysis, Oxidized lipid Analysis

Table 1. Schedule of Assessments

Schedule of Assessments	Screening	Baseline/ Randomization	Week 2	Week 4	Week 8	Week 12
Visit Number	1	2	3	4	5	6
Visit Window		± 7-28 Days	± 4 Days	± 7 Days	± 7 Days	± 7 Days
Informed consent	X					
Demographics & Medical history	X					
Vital signs (HR, BP)	X	X	X	X	X	X
ECG	X					
Review for AEs/SAEs/CV events		X	X	X	X	X
Concomitant therapy	X	X	X	X	X	X
Dietary instruction; medication compliance reminder	X	X	X	X	X	
Physical examination	X					
Body height, waist circumference	X					X
Body weight	X					X
Seattle Angina Questionnaire 7 (SAQ7)	X	X	X	X	X	X
Placebo Injection	X					
Laboratory Analyses:						
TSH	X					
Hematology (CBC)	X		X			X
Chemistry (creatinine/eGFR, electrolytes)	X		X			X
Liver Function Tests (AST, ALT)	X		X			X
Urine albumin to creatinine ratio (ACR)	X					X
HbA1c	X					
Local Lipid Panel	X					
Urine pregnancy (if applicable)	X					
Fibrinogen		X	X			X
lipoprotein(a), Apo B		X	X			X
Whole Blood Viscosity Analysis		X	X			X
NMR Lipoprotein Subclass Analysis		X	X			X
Biocellular Marker Analysis		X	X			X
Oxidized lipid Analysis		X	X			X
DNA/mRNA test		X				
Randomization		X				

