7.3 Primary efficacy analysis

The primary efficacy comparison between groups will be by means of linear regression (ANCOVA model). The point estimate of the effect and 95% confidence interval will be obtained, after adjustment for the baseline values. The primary analysis will be ITT. These analyses are viewed as complementary or exploratory, so the interest will be on the estimated treatment effects more than actual hypothesis tests.

Protein immunoblots will be analyzed using ImageJ software. Gene expression will be analyzed using comparative Ct method ($\Delta\Delta Ct$) and normalized to GAPDH.

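### The Week 2 versus Week 12 comparison in Section 7.2 cannot show how rheological change relates to biocellular markers, and Section 7 has no analysis of the viscosity-mediator association planned in the background

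*Combined protocol and SAP*

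**What the plan says.** Four places in the combined protocol and SAP bear on this.

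- **Background (text before Section 1.1).** An exploratory aim is to "examine the associations between baseline and on-trial change in low shear blood viscosity with inflammatory mediators".
- **Section 1.1.1.** The primary objective covers the "effects of PCSK9 inhibition with evolocumab on biocellular markers of inflammation, immune mediated thrombosis and rheology", so rheology is itself an outcome domain.
- **Section 7.2.** Week 2 and Week 12 are each compared with baseline. A second sentence adds: "We will also compare week 2 with week 12 to identify how the expected rheological changes may impact biocellular responses". It does not say which variables enter that comparison, or whether it is made within or between arms.
- **Section 7.3.** The only statistical model is a between-group ANCOVA: "The point estimate of the effect and 95% confidence interval will be obtained, after adjustment for the baseline values". The section describes the analyses as exploratory, with more interest in estimates than in tests.

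On data, Section 4 and Table 1 schedule "whole blood viscosity analysis, NMR lipoprotein subclass analysis, Apo B, lipoprotein (a), biocellular marker analysis, Oxidized lipid Analysis" at Visits 2, 3 and 6, that is at baseline, Week 2 and Week 12. Paired viscosity and marker values will therefore exist for each person at each of these times. On size, Section 3.1 states: "Approximately 100 subjects will be screened in order to keep 40 subjects to complete the study".

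**The concern.** The second sentence of Section 7.2 gives a comparison over time the job of answering a question about association. A difference in a marker between Week 2 and Week 12 shows that the marker changed. It does not show that the change had anything to do with viscosity. A report that followed the sentence as written could present a time difference as an effect of rheology, although the same means are compatible with any within-person relation between viscosity and marker, including none.

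The background names the analysis that would address the relation, but Section 7 does not carry it forward: there is no model, covariate set or interval for it. Section 7.1 says that the results will support the sizing of a larger trial, so a misattributed signal could be carried into that planning.

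**Working it through.** **1. Does any analysis in Section 7 relate viscosity to a marker?** Section 7.1 gives the sample size rationale. Section 7.2 gives comparisons between visits. Section 7.3 gives a between-group ANCOVA adjusted for baseline, followed by the processing of immunoblots and gene expression. The ANCOVA can estimate the drug's effect on viscosity, or on a marker, taken one outcome at a time. None of the three sections contains a correlation, a regression of marker on viscosity, or a mediation analysis.

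**2. Can a comparison of visits stand in for one?** There are two readings.

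- *Only markers are compared.* Viscosity does not enter, so reassigning viscosity values among participants leaves the result unchanged.
- *Markers and viscosity are both compared.* Each mean difference is computed separately. Reassigning one person's viscosity change to another leaves both means as they were, while the within-person relation can become anything.

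A simulation illustrates this. With 40 people and a mean marker change of -0.30 SD between two visits (SD of the change), the estimate was -0.30 with standard error 0.157, both when the viscosity-marker correlation was 0 and when it was 0.6.

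**3. What would the missing analysis deliver at this size?** The plan states no figure to reproduce. Inputs: n = 40 (Section 3.1), assumed all with paired data; three covariates (arm, baseline mediator, baseline viscosity); Fisher z interval.

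- SE = 1/√(40 - 3 - 3) = 0.171, and 1.96 × 0.171 = 0.336.
- Observed partial correlation 0.3: tanh(0.3095 ± 0.336) = -0.03 to 0.57.
- Smallest observed value whose interval excludes 0: tanh(0.336) = 0.32.
- True value giving an 80% chance of that: tanh((1.96 + 0.8416) × 0.171) = 0.45.
- Baseline association without covariates: SE = 1/√(40 - 3) = 0.164, so an observed 0.3 has an interval of -0.01 to 0.56.

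**4. Precision of the Week 12 minus Week 2 contrast between arms.** The allocation ratio is not given numerically, so 20 per arm is an assumption, as is the within-person correlation r. In SD units, the 95% half-width is t₃₇ × √(2(1 - r)) × √(2/20). This gives 0.76 at r = 0.3, 0.64 at r = 0.5 and 0.50 at r = 0.7.

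**5. What else differs between the two visits?** Table 1 places injections at baseline, Week 4 and Week 8. "Visit 3 (Week 2) ±4 days" puts the Week 2 sample 14 ± 4 = 10 to 18 days after the first injection. "Visit 5 (Week 8) ±7 days", with the same ±7-day window at Week 12, puts the Week 12 sample nominally 84 - 56 = 28 days after the third injection, with a range from 77 - 63 = 14 to 91 - 49 = 42 days. The visit difference therefore mixes treatment duration, number of doses and time since injection.

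**The case against.** The strongest reply is that the plan calls itself signal-finding, labels the viscosity association exploratory and prefers estimates to tests, so a fully written model is more than such an aim needs. This stands as a limit on weight. It does not rescue the sentence in Section 7.2, which names a method for a question that the method cannot answer.

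The documents do not support several stronger readings that a reader might infer.

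- *The comparison uses markers only.* Section 7.2 does not say which variables are compared. Viscosity is measured at the same visits and rheology is in the primary objective, so viscosity may be compared too. The point holds either way.
- *The Week 12 minus Week 2 difference is uncontrolled.* The text does not tie it to placebo in so many words. However, Section 3.1 describes a randomized, placebo-controlled, parallel-group design and Section 7.3 specifies a between-group model. Saying that the contrast is between arms is a clarification and does not correct an error.
- *The drug's effect on rheology goes unanalysed.* The Section 7.3 model can take viscosity as an outcome. Only the viscosity-marker relation lacks an analysis.
- *The different times since injection are a design fault.* They are a reason for care in reporting and no more.

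It is also fair to object that a regression adjusted for arm answers a different question from the one in Section 7.2, because its slope uses variation within arms and is not the effect of a viscosity change caused by the drug. This stands, and the proposed wording says so. Finally, the secondary association objectives in Section 1.1.2 also have no method in Section 7. That is a separate matter and does not remove this one.

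**Conclusion.** The concern holds as a minor point about exploratory analyses. The visit comparison does not answer the rheology question that Section 7.2 gives it, and the association planned in the background has no analysis in Section 7. This conclusion rests on the text and on what a difference of means can show. It does not depend on the sample size or on any assumed correlation.

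The primary between-group comparison is unaffected. The practical risk is one of interpretation: a difference between early and late values could be reported as a consequence of rheology. The precision figures assume that all 40 participants contribute paired data, and the contrast between arms also assumes 20 per arm.

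**What to change.** In Section 7.2, keep the Week 2 versus Week 12 comparison as a description of early versus late change. State that it is evolocumab minus placebo, estimated with the baseline-adjusted model of Section 7.3, and drop the stated rheology purpose. Then add:

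> For each inflammatory mediator, change from baseline to Week 2 and, separately, to Week 12 will be regressed on change in low-shear blood viscosity over the same interval, with arm, baseline mediator and baseline viscosity as covariates; the association of baseline viscosity with baseline mediator will also be estimated. Slopes are reported with 95% CIs as exploratory associations, not as the effect of a drug-induced viscosity change, beside the between-arm effect on viscosity.

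The mediators should be listed by name. Arm is a covariate because pooling the arms without it could create an association through treatment alone. The baseline association is included because the background plans it. The between-arm effect on viscosity lets a reader see whether the expected rheological change occurred. When Week 2 and Week 12 are compared, the report should note that they differ in number of doses and time since injection as well as in duration.

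**Cost.** Only analysis and reporting text changes; visits, sampling and dosing stay as they are. The association will be imprecise at n = 40, measurement error in viscosity will pull the slope toward zero, and unmeasured common causes of viscosity and mediator change remain possible.
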